11.2.2 Assessment of Causality

The Investigator will assess the potential causal relationship of each event, using clinical judgement. Alternative causes, such as natural history of underlying diseases, other risk factors and the temporal relationship of the event to the IMD and/or comparator product will be considered and investigated. The causal relationship to the IMD and/or comparator is to be assessed by the Investigator (or medically qualified delegate) and should be assessed using the following classifications:

Table 4. Potential causal relationship of event.

Not related	Relationship to the medical device or procedures can be excluded when: 
the event is not a known side effect of the product category the device belongs to or of similar devices and procedures;the event has no temporal relationship with the use of the device or the procedures;the event does not follow a known response pattern to the medical device (if the response pattern is previously known) and is biologically implausible;the discontinuation of medical device application or the reduction of the level of activation/exposure - when clinically feasible - and reintroduction
-------------	---

	
of its use (or increase of the level of activation/exposure), do not impact on the event;
 
 • the event involves a body-site, or an organ not expected to be affected by the device or procedure; • the event can be attributed to another cause (e.g. an underlying or concurrent illness/ clinical condition, an effect of another device, drug, treatment or other risk factors); • the event does not depend on a false result given by the investigational medical device used for diagnosis, when applicable; • harms to the subject are not clearly due to use error; 
In order to establish the non-relatedness, not all the criteria listed above might be met at the same time, depending on the type of device/procedures and the event.

Unlikely related	
The relationship with the use of the medical device seems not relevant and/or the event can be reasonably explained by another cause, but additional information may be obtained.

Possibly related	
The relationship with the use of the medical device is weak but cannot be ruled out completely. Alternative causes are also possible (e.g., an underlying or concurrent illness/ clinical condition or/and an effect of another device, drug or treatment). Cases where relatedness cannot be assessed, or no information has been obtained should also be classified as possibly related.

Probably related	
The relationship with the use of the medical device seems relevant and/or the event cannot be reasonably explained by another cause, but additional information may be obtained.

Definitely related	
The event is associated with the medical device or with procedures beyond reasonable doubt when:
 
 • the event is a known side effect of the product category the device belongs to or of similar devices and procedures; • the event has a temporal relationship with the medical device use/application or procedures; • the event involves a body-site or organ that 
 – the medical device or procedures are applied to – the medical device or procedures have an effect on; • the event follows a known response pattern to the medical device (if the response pattern is previously known); • the discontinuation of medical device application (or reduction of the level of activation/exposure) and reintroduction of its use (or increase of the level of activation/exposure), impact on the event (when clinically feasible); • other possible causes (e.g., an underlying or concurrent illness/ clinical condition or/and an effect of another device, drug or treatment) have been adequately ruled out; • harm to the subject is due to error in use; • the event depends on a false result given by the medical device used for diagnosis, when applicable; 
In order to establish the relatedness, not all the criteria listed above might be met at the same time, depending on the type of device/procedures and the event.

11.2.3 Assessment of Seriousness

The Investigator will assess the seriousness of each event according to clinical judgement and the definition provided in section 11.1.3.

11.2.4 Assessment of Expectedness

An event should be considered unanticipated if the nature, severity, or frequency of that event is not consistent with the applicable safety reference information, such as the risk analysis report, hazards analysis, IB, or Product Information/IFU if the product is approved for marketing.

For this clinical investigation the listed items in Section 8.2 and 8.3 of this CIP and/or the Investigator's Brochure> are anticipated ADEs.

Table 5. Assessment of Expectedness.

Anticipated	An adverse device effect (ADE) which by its nature, incidence, severity, or outcome is consistent with the applicable safety reference information (e.g., IB, IFU).
Unanticipated	An adverse device effect (ADE) which by its nature, incidence, severity, or outcome is not consistent with, or has not been identified in the applicable safety reference information (e.g., IB, IFU).

11.3 Recording and Handling of Device Deficiencies

Subjects shall be carefully monitored during the clinical investigation and routinely questioned about DDs at investigation visits. Source notes should indicate the evaluation for DDs, even if none to report.

The Investigator shall assess if the DD led to an AE or could have led to a serious medical occurrence (serious adverse device effect) if;

- a) suitable action had not been taken,
- b) intervention had not been made, or,
- c) circumstances had been less fortunate

All DDs will be documented in the source notes and the DD page of the CRF.

11.4 Reporting Responsibilities

The Investigator is responsible for reporting all AEs and DDs in the CRF.

11.4.1 Investigator Reporting of Serious Adverse Events

All AEs meeting the criteria for an SAE, or DD that could have led to an SADE, must be reported to the Sponsor during the same working day.

Reporting is achieved through completion of the events details in the Adverse Event page of the eCRF

The Investigator shall always provide an assessment of causality at the time of the initial report, as described in section 11.2.2 'Assessment of Causality'. If data obtained after reporting indicates that the assessment of causality is incorrect, then the SAE form may be appropriately amended, signed, dated, and resubmitted to the Sponsor.

If the Investigator does not have all other information regarding an SAE, he/she will not wait to receive additional information before reporting the event. The reporting forms shall be updated when additional information is received.

The Investigator is responsible for reporting of safety events to their local EC using the applicable report form, in accordance with local regulations.

11.4.2 Sponsor Notification of Events

The Sponsor is responsible for reviewing all safety data to evaluate potential causality and anticipation of all ADEs. SAEs will be reported in accordance with MEDDEV 2.7/3, revision 3, May 2015 (10):

The sponsor must report to the NCAs where the clinical investigation has commenced:

- for all reportable events as described in section 4 which indicate an imminent risk of death, serious injury, or serious illness and that requires prompt remedial action for other patients/subjects, users or other persons or a new finding to it: immediately, but not later than 2 calendar days after awareness by sponsor of a new reportable event or of new information in relation with an already reported event.

- any other reportable events as described in section 4 or a new finding/update to it: immediately, but not later than 7 calendar days following the date of awareness by the sponsor of the new reportable event or of new information in relation with an already reported event.

The Sponsor is also responsible for reporting all reportable events according to the requirements and timelines of the regulatory authorities relevant to this clinical investigation, and shall conduct an expedited assessment of all SAEs, unanticipated ADEs, DDs that could have led to an SADE.

The Safety Monitor for AE/DD assessment and any AE/DD related queries is:

Name Sponsor Safety Monitor:	[REDACTED] [REDACTED]
Country:	Sweden
Phone number:	[REDACTED]
E-mail:	[REDACTED]

11.5 Independent Data Monitoring Committee

Not applicable.

12 DEVICE ACCOUNTABILITY

Supply of investigational medical devices will be recorded using the Sponsor Device Tracking Form (1295388). Investigational medical device(s) will be quarantined at the investigational site and clearly labelled to identify exclusively for use in a clinical investigation.

Subject level device supply will be tracked in the CRF.

13 DEVIATIONS FROM THE CLINICAL INVESTIGATION PLAN

The Investigator(s) must not deviate from the CIP, except in case of an emergency to protect the safety and well-being of the subject(s). Such deviations will be documented by the site personnel in the source documentation for the subject and reported to the relevant EC as per institutional requirements and to the Sponsor as soon as possible, but not later than 24 hours from the date of the emergency.

If there is a deviation from CIP-defined assessments or parts thereof are omitted or completed incorrectly, the deviation will also be documented by the site personnel in the source documentation for the subject. Depending on the type or severity of the deviation the Investigator may be required to notify the EC, particularly if the deviation potentially impacts subject safety, performance of IMD and/or comparator, or data integrity.

All CIP deviations will be documented in the eCRF to enable analysis and reporting by the Sponsor in the Clinical Investigation Report, or to the relevant regulatory authority(s), if applicable.

Gross misconduct on behalf of an Investigator, such as intentional non-compliance with CIP or GCP requirements or fraud, will result in disqualification of the Principal Investigator and/or Investigational Site from participation in the investigation. Data provided by the Principal Investigator or Investigational Site will be excluded from the per-protocol analysis group.

14 DATA MANAGEMENT

The CRF will capture subject status according to the following criteria:

- **Consented:** Signed consent and eligibility evaluations underway
- **Screen Fail:** Subject determined not to be eligible to proceed for participation
- **Enrolled:** First use of the IMD or comparator following completion of screening activities and confirmation of eligibility
- **Withdrawn:** Enrolled subjects who withdraw or are withdrawn by the Investigator or Sponsor before the expected End of Study visit. Withdrawn subjects may continue in safety follow up until their scheduled End of Study visit.
- **Complete:** Enrolled subjects who complete the planned follow up schedule and End of Study visit.

Source data will be captured in clinic notes, paper-based source data worksheets, or printed directly from testing software.

Data collection will be performed using [REDACTED] for electronic data capture (EDC) on electronic Case Report Forms (eCRFs). Site staff will be trained on the completion of the eCRFs prior

to obtaining access to the system and will have their own Login/Password. Access to clinical study information will be based on an individual's role and responsibilities.

████████ uses role-based user permissions for data entry, viewing, and reporting options. All communications between users and the EDC server are encrypted. Web servers are protected by a managed firewall. This application is designed to be in compliance with applicable regulations including 21 CFR Part 11.

The application will include programmed data consistency checks and supports manual generation of data clarifications/queries, including documentation of site responses. The application maintains a comprehensive audit trail for all data entered, including updates and queries, and documents the time that each entry occurred and who made the entry.

Principal Investigators will affirm that the data for each subject at their site is accurate and complete by way of an electronic signature.

15 CONFIDENTIALITY

The investigator and site staff will collect and process personal data of the subjects in accordance with governing data privacy regulations [such as the EU GDPR regulations].

Data will be reported to the Sponsor on CRFs or related documents (for example, questionnaires). Subjects will be identified on CRFs and other related documents only by a unique subject identification code and shall not include the subject's name or other personal identifiable information. Completed CRFs or related documents are confidential and will only be available to the Investigator and site staff, the Sponsor and their representatives, and if requested to the Ethics Committee and national regulatory authorities. Publications or submission to a regulatory authority shall not disclose the identity of any subject.

16 ETHICS COMMITTEE AND REGULATORY AUTHORITY APPROVAL

The clinical investigation will not commence prior to the written favourable opinion or approval from the EC and or regulatory authority (if appropriate) is obtained.

The final Sponsor-approved version of the CIP, Informed Consent Form, and other necessary documents shall be submitted to the EC. A copy of the EC opinion/approval shall be provided to the Sponsor.

The Investigator shall forward to the Sponsor, for review and approval, any amendment made to the approved ICF and any other written information to be provided to the subject prior to submission to the EC.

The Sponsor and Principal Investigator will continue communications with the EC, as required by national regulations, the clinical investigational plan, or the responsible regulatory authority.

Any additional requirements imposed by the EC or regulatory authority will be implemented by the Sponsor.

The Investigator shall submit the appropriate documentation if any extension or renewal of the EC approval is required. Substantial amendments to the CIP, the ICF, or other written information provided to subjects will be approved in writing by the EC.

The Investigator shall report to the EC any new information that may affect the safety of the subjects or the conduct of the clinical investigation. The Investigator will send written status summaries of the investigation to the EC regularly, as per local EC requirements.

Upon completion of the clinical investigation, the Investigator shall provide the EC with a brief report of the outcome of the clinical investigation, as per local EC requirements.

The clinical investigation is covered by clinical trial insurance, meeting the requirements of the participating countries.

17 SUSPENSION OR PREMATURE TERMINATION

The Sponsor will discontinue the clinical investigation site if:

- 1) major non-adherence to the CIP or GCP principles is occurring
- 2) it is anticipated that the subject recruitment will not be adequate to meet the objectives of the clinical investigation

An ongoing clinical investigation may be discontinued in case of:

- 1) device failure
- 2) serious or intolerable ADE, leading to the explant or discontinued use of the device
- 3) subject's death

17.1 Reporting to regulatory authority

If this investigation is suspended or terminated prematurely, the Swedish Medicines Agency shall be informed within 24 hours whether it is for safety reasons that the trial is terminated or cancelled, otherwise within 15 calendar days. When a trial is completed according to plan, the Swedish Medicines Agency must be informed within 15 calendar days after the trial has ended (last subject last visit).

18 AMENDMENTS TO THE CLINICAL INVESTIGATION PLAN

No changes in the CIP or investigation procedures shall be made without mutual agreement of the Principal Investigator and the Sponsor. This agreement will be documented as a CIP amendment. Amendments will require notification to the Ethics Committees (ECs) by the Principal Investigators (and to the relevant regulatory authority(s) by the Sponsor, if applicable).

19 RECORD KEEPING AND RETENTION

Data generated from the clinical investigation will be stored in a limited-access file area and be accessible only to representatives of the study site, the Sponsor and its representatives, and relevant health authorities/regulatory agencies. All reports and communications relating to study subjects will identify subjects only by subject unique identification code. Complete subject identification will be maintained by the Investigator. This information will be treated with strict adherence to professional standards of confidentiality.

The investigator must retain study-related records for a period of at least 15 years after completion of the investigation or after the last device was placed on the market, if the IMD has market authorisation.

20 PUBLICATION POLICY

This clinical investigation will be prospectively registered at a public clinical trial registry, i.e. ClinicalTrials.gov.

A joint peer-reviewed publication authored by the clinical investigator(s) and Sponsor will be prepared. In addition, the results of the clinical investigation (8) (9) may also be disseminated as conference presentations (e.g., abstract and poster session). Manuscript authorship and responsibilities will be discussed and agreed upon prior to investigation start and in accordance with guidelines and recommendations provided by the International Committee of Medical Journal Editors (ICMJE) to enable communication in a timely manner. All contributors who do not meet the criteria for authorship will be listed in an acknowledgments section of the publication.

21 STATEMENTS OF COMPLIANCE

This clinical investigation shall be conducted in accordance with ethical principles that have their origin in the Declaration of Helsinki (11), International Standard ISO 14155 Clinical investigation of medical devices for human subjects - Good Clinical Practice (1), and any regional or national regulations, as applicable.

22 QUALITY CONTROL AND ASSURANCE

In accordance with Cochlear's Quality Management System, all clinical investigations shall be conducted according to internationally recognised ethical principles for the purposes of obtaining clinical safety and performance data about medical devices.

The Sponsor employees (or designee) shall use standard operating procedures (SOP) to ensure that clinical study procedures and documentation are consistently conducted and compliant with the ISO 14155 Standard, Good Clinical Practice (GCP) (1), and applicable local regulations.

22.1 Monitoring

The Sponsor will perform on-site and remote monitoring visits as frequently as necessary to oversee conduct, data collection and record keeping by sites. The clinical investigation monitoring plan is a separate document describing all the activities performed during initiation, monitoring, and close out>.

22.2 Audits

An Investigator must, in reasonable time, upon request from a relevant health authority or regulatory agency, permit access to requested records and reports, and copy and verify any records or reports made by the Investigator

22.3 Trademarks and Copyright

ACE, Advance Off-Stylet, AOS, AutoNRT, Autosensitivity, Beam, Button, CareYourWay, Carina, Cochlear, 科利耳, コクレア, Cochlear SoftWear, Codacs, ConnectYourWay, Contour, Contour Advance, Custom Sound, ESPrit, Freedom, Hear now. And always, HearYourWay, Hugfit, Hybrid, Invisible Hearing, Kanso, MET, MicroDrive, MP3000, myCochlear, mySmartSound, NRT, Nucleus, Off-Stylet, Slimline, SmartSound, Softip, SPrint, True Wireless, the elliptical logo, WearYourWay and Whisper are either trademarks or registered trademarks of Cochlear Limited. Ardiim, Baha, Baha SoftWear, BCDrive, DermaLock, EveryWear, VistaFix, and WindShield are either trademarks or registered trademarks of Cochlear Bone Anchored Solutions AB. © Cochlear [2020]

1 INTRODUCTION

This document is a companion document to the Clinical Investigation Plan (CIP). It includes a comprehensive description of the intended statistical analyses to be performed and the presentation of the results and data collected for the study.

This Statistical Analysis Plan (SAP) is based upon final CIP version 3.0

Any deviation from the Statistical Analysis Plan will be reported in the Clinical Investigation Report (CIR).

2 STUDY POPULATION

The subjects include men and women aged 18 or older who are currently using the Baha Connect System (percutaneous Baha). Subjects will be screened, and 16 eligible subjects will be enrolled in the clinical investigation.

3 STUDY ENDPOINTS

3.1 Endpoints to be used for the primary objectives

- First primary objective: Adaptive speech in noise [signal-to-noise ratio, 50% speech understanding]
- Second primary objective: Preference of device.

3.2 Endpoints to be used for the secondary objectives

- Daily use of sound processors (hours) from Diary, Only Baha 6 Max SP vs Baha 5 SP
- Change of battery from Diary, Only Baha 6 Max SP vs Baha 5 SP
- Switch to their own sound processor and the reason for change from Diary (Only Baha 6 Max SP vs Baha 5 SP)
- Adaptive speech in noise [signal-to-noise ratio, 50% speech understanding] Baha 6 Max SP and Baha 5 SP
- Thresholds audiology, sound-field [0.25, 0.5, 1.0, 2.0, 3.0, 4.0, 6.0, 8.0 9.0 and 10.0 kHz]
- Speech in quiet [% correctly perceived words at 65dB SPL]
- Evaluation of sound quality and listening effort through sound clips. Only Baha 6 Max SP and Baha 5 SP.

4 STATISTICS

4.1 Sample Size

In order to meet the sample sizes calculations for both primary analyses, 16 subjects will be included.

As this is an internal Cochlear investigation, patients will be recruited until the number of required patients are enrolled. Hence, no dropouts are expected.

First primary analysis: Baha 6 Max SP vs unaided regard Adaptive speech in noise

From the CIP: Assuming an individual mean difference (aided Baha 6 Max SP minus unaided) in speech recognition in noise of 16 dB SNR with a standard deviation (SD) of 12.5 (Busch et al, 2015),

a total sample of 15 eligible subjects are required to provide 90% power to reject the null hypothesis for the statistical test for the primary objective (change in dB SNR) using a two sided, alpha 0.0050, with Two-sided Fisher's non-parametric permutation test for paired observations.

4.2 Analyses

4.2.1 Pass/Fail Criteria

If the signal-to-noise-ratio for a subject is at least 50% regarding speech understanding the subject will be classified as a responder. The primary objective of the study is that the null-hypothesis that the proportion of responders for the Baha 6 Max SP and the Baha 5 SP are equal.

If the two-sided p-value when testing the hypothesis above is below 5% the results of the study are considered successful.

This means that the pass/fail criteria for each subject is speech understanding and the pass-criteria is that the signal-to-noise-ratio for a subject is at least 50%.

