7.3.3 Adaptive Speech recognition in noise (Matrix test)

The purpose of this test is to establish the test subject's ability to recognise speech in the presence of background noise. The adaptive speech test in noise shall be conducted using validated lists of phonetically balanced sentences, with speech presented in sound-field from the front (0 degrees azimuth) and noise will also be presented from the front (figure 4). The noise shall be kept constant at 65 dB SPL, and the speech shall be adapted stepwise according to the software used to establish the speech-to-noise ratio (SNR) providing a 50% level of understanding.

Software and speech material to be used is the Matrix test in language specific versions as applicable.

The test shall be performed with the non-test ear blocked (in case of normal or near-normal hearing or a large asymmetry with the non-test ear having significantly better hearing thresholds).

The speakers should be at the height of the test subjects head and more than 1 metre away from the test subject. There should preferably be more than 1 metre of free space around the test subject in all directions. This is in accordance with the current standard.

FRONT

Figure 5: Speech in noise speaker position

At Visit 1 and 2, the speech in noise test will be performed for the aided situation with Baha 6 Max SP or Baha 5 SP depending on the randomisation order.

At visit 3 the test will be performed unaided.

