4.2.2 Primary Hypothesis

The first primary efficacy objective is the comparison regarding adaptive speech in noise. If the signal-to-noise-ratio for a subject is at least 50% regarding speech understanding the subject will be classified as a responder. The null-hypothesis that the proportion of responders for the Baha 6 Max SP and the Baha 5 SP are equal will be tested using the Binomial test.

The second primary efficacy analysis is to test the null-hypothesis that the proportion of subjects who prefer Baha 6 Max SP and the proportion of subjects who prefer Baha 5 SP are equal will be tested using the Binomial test.

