4.3 Analysis Datasets

4.3.1 Intent-to-Treat

The Full Analysis Set will consist of all correctly included and randomized subjects that have at least one measurement on two of the periods Baha 6 Max SP Baha 5 SP.

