4.4 Additional Statistical Considerations

4.4.1 Missing, Unused or Spurious Data

No imputation of missing data will be performed, i.e. an observed case approach will be used in the statistical analyses.

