4.4.4 Additional Statistical Analyses

No additional analysis will be conducted.

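### The SAP's primary responder rule (SNR of at least 50%) cannot be computed from a test whose result is in dB, and it displaces the protocol's primary comparison with unaided hearing

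*SAP*

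**What the plan says.** **The measurement.** Protocol 7.3.3 uses a fixed noise level of 65 dB SPL. For the signal, its instruction is: "the speech shall be adapted stepwise according to the software used to establish the speech-to-noise ratio (SNR) providing a 50% level of understanding". The two aided runs are at Visits 1 and 2 and the unaided run is at Visit 3.

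**The protocol's first primary analysis (9.3.1, 9.6).** This is Baha 6 Max against unaided, by a two-sided paired permutation test of the SNR at 0.005, reported as a mean difference with a 99.5% confidence interval. Device preference is the second primary analysis, at 0.045. Sections 9.1 and 9.6 link the two by a Holm-type rule, under which one may be retested at 5% if the other is significant.

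**The SAP's sample size (4.1).** It keeps the protocol's contrast: "First primary analysis: Baha 6 Max SP vs unaided regard Adaptive speech in noise", with a difference of 16 dB, SD 12.5, two-sided alpha 0.0050, 15 subjects and 90% power.

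**The SAP's analysis (4.2.1, 4.2.2).** The responder rule is "If the signal-to-noise-ratio for a subject is at least 50% regarding speech understanding the subject will be classified as a responder". Section 4.2.2 then sets the first primary test as a comparison of the two devices, with this null: "the proportion of responders for the Baha 6 Max SP and the Baha 5 SP are equal will be tested using the Binomial test". On success, 4.2.1 says: "If the two-sided p-value when testing the hypothesis above is below 5% the results of the study are considered successful". Preference is tested in 4.2.2 but does not enter that criterion.

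**Elsewhere in the SAP.** Section 4.2.3 tests only the two devices against each other. Section 4.3.1 defines the full analysis set by "at least one measurement on two of the periods Baha 6 Max SP Baha 5 SP", while 4.3.2 requires data from all three periods for the per-protocol set. On missing data, 4.4.1 says: "No imputation of missing data will be performed, i.e. an observed case approach will be used in the statistical analyses". Section 4.4.4 says: "No additional analysis will be conducted".

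**The concern.** The responder rule compares a quantity in dB with a percentage. The percentage it uses is a constant of the test procedure, the same for every subject and every condition, so it cannot separate one subject or device from another. The wording appears twice in 4.2.1 and again in 4.2.2, so it is hard to treat as a single slip.

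The contrast with unaided hearing is the one that protocol 7.1.1 ties to regulatory approval. If SAP 4.2 is followed, that contrast is not tested. Its replacement needs a rule that someone would have to invent at analysis, in a study whose speech-in-noise testing is open label. The SAP's only statement of what counts as success is attached to that replacement.

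**Working it through.** **1. The plan's own sample size.** Inputs from protocol 9.4 and SAP 4.1: difference 16 dB, SD of the paired difference 12.5 dB, two-sided alpha 0.005. A paired t-test with the noncentral t distribution serves as a close stand-in for the permutation test. The noncentrality is (16/12.5) × √n = 1.28 × √n, and power is P(|T| > t(0.9975, n−1)).

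| n | noncentrality | critical t | power |
|---|---|---|---|
| 14 | 4.789 | 3.372 | 89.2% |
| 15 | 4.957 | 3.326 | 92.4% |
| 16 | 5.120 | 3.286 | 94.7% |

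The smallest n with at least 90% power is 15, as stated. A simulation of the sign-flip permutation test on normal data (1,500 runs per n) gave 88.1%, 91.1% and 93.6% at n = 14, 15 and 16. The sample size is sound for the dB contrast with unaided.

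**2. Applying the responder rule literally.** Each subject and condition yields one number, the SNR in dB at which understanding is 50%. The rule needs either a dB threshold or a percentage that varies between subjects. Neither document gives a dB threshold, and the percentage is fixed by design. No subject can be classified.

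**3. Applying the nearest workable reading.** Suppose a responder is a subject whose run reached the 50% target. Every completed run then qualifies.
- With 16 subjects complete on both devices, responders are 16/16 and 16/16.
- In a paired form, discordant subjects = 16 − 16 = 0, so the exact two-sided p = 1. The SAP says only that a Binomial test is used, so pairing is an assumption.
- In an unpaired exact comparison of 16/16 with 16/16, p = 1 as well.

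If a run did not complete and was left out under the observed-case approach of SAP 4.4.1, the remaining pairs would still all be concordant.

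**4. The two first primary analyses side by side.**

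| | Protocol 9.3.1, 9.6 | SAP 4.2.1, 4.2.2 |
|---|---|---|
| Comparator | unaided | Baha 5 |
| Scale | SNR in dB | responder yes/no |
| Test | paired permutation | Binomial |
| Alpha | 0.005, within the 0.005/0.045 rule | 5%, unconditional |
| Estimate | mean difference, 99.5% CI | none stated |

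**5. Consistency within the SAP.** Section 4.1 names the unaided contrast as the first primary analysis, with its test and alpha, and 4.3.2 presupposes an unaided period. No test in 4.2 uses that period, and 4.4.4 closes the list of analyses. No power is stated for a responder comparison with Baha 5. None can be derived, because the documents give neither a cut-off nor responder rates.

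**The case against.** The strongest defence is that the SAP has not abandoned the protocol's analysis. Section 4.1 repeats it with comparator, test and alpha, 4.3.2 needs all three periods, and 3.1 keeps the SNR endpoint. A reader might infer from 4.2 that the unaided contrast has no place in the SAP; that is too strong. What stands is that the SAP contradicts itself: the contrast is named in the sample size section and missing from the section that says what will be tested.

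Other points limit the concern:
- **Analysis set.** Section 4.3.1 names only the device periods, but this does not by itself block the unaided analysis. Unaided testing comes last, so a subject with unaided data would normally have both device measurements and be in the set already. It is a point of consistency.
- **The 5% level.** It is not foreign to the protocol, since 9.6 permits a retest at 5% after the other primary succeeds. The defect is that the SAP applies it unconditionally.
- **Success wording.** Section 4.2.1 says when results count as successful. Despite its pass/fail heading, it does not say that the study otherwise fails.
- **Timing.** A reader might infer from the SAP date of 3-Mar-2021 that the primary analysis was changed with data in hand. The documents do not support that. The SAP change history says the original was released on 22-Oct-2020 and that the March version moved it into a template. Protocol section 2 expected a start in early September 2020 and 8 weeks in total, so October could fall within the study. Actual dates are not given, nor which version introduced the responder text.

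A version difference does not rescue the SAP. It cites protocol version 3.0, and the protocol's change history lists only section 8.4 as altered in version 4.0.

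**Conclusion.** The concern holds and must be fixed. The responder rule cannot be computed as written. On the reading closest to protocol 7.3.3 it gives 0 discordant subjects and p = 1 whatever the devices do; that result is conditional on the reading and on completed runs. SAP 4.2 changes the first primary analysis in comparator, scale, test and alpha, and specifies no test against unaided, in conflict with SAP 4.1.

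A reader might also infer that the trial is underpowered or that its data cannot answer the primary question. Neither follows. The stated 15 subjects reproduce for the protocol's analysis, the planned 16 give about 95% power under the protocol's assumptions, and all three conditions are measured. The secondary dB comparison with Baha 5 does not depend on the responder rule, and preference is still tested. The fault is confined to the SAP's primary analysis and success criterion.

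**What to change.** In SAP 4.2.1 and 4.2.2:
- Remove the responder rule, and the 5% success criterion attached to it, as the primary analysis.
- Restore the analysis of protocol 9.3.1 and 9.6: a two-sided paired permutation test of SNR in dB, Baha 6 Max against unaided, at alpha 0.005, with mean difference and 99.5% confidence interval.
- Base the success statement on the protocol's two primary analyses, speech in noise against unaided and preference, under the rule in 9.1 and 9.6. The sponsor should state whether one or both are required.
- Keep the dB comparison of Baha 6 Max with Baha 5 as secondary. If a responder analysis is wanted, define it in dB and label it supplementary.

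For consistency, name the unaided period in the SAP 4.3.1 analysis set, as protocol 9.5.1 does.

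The cost is a dated SAP revision; no new data or visits are needed. The revision should record the change as a return to the protocol's prespecified analysis and give both SAP dates (22-Oct-2020 and 3-Mar-2021). It should also say whether it came before or after database lock, since protocol 9.11 requires the SAP to be signed off before lock.
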